1.0 STUDY SYNOPSIS

Protocol:

IDN-6556-07

Title:

A Multicenter, Double-Blind, Randomized Trial of IDN-6556 in Subjects Who had Hepatitis C Virus (HCV) Reinfection and Liver Fibrosis or Cirrhosis Following Orthotopic Liver Transplantation for Chronic HCV Infection and Who Subsequently Achieved a Sustained Virologic Response Following anti-HCV Therapy

Phase of Trial:

Phase 2

Objectives:

Primary

- To assess the effect of oral IDN-6556 on fibrosis or cirrhosis using the Ishak Fibrosis Score, in subjects with HCV reinfection and liver fibrosis or cirrhosis following orthotopic liver transplantation for chronic HCV who subsequently achieved a sustained virologic response following anti-HCV therapy

Secondary

- To determine the effects of oral IDN-6556 on necro-inflammatory sub-score of the modified Histological Activity Index
- To determine the effects of oral IDN-6556 on markers of mechanism of action and inflammation
- To assess the safety and tolerability of oral IDN-6556 in subjects status post orthotopic liver transplantation

Centers:

Multicenter, approximately 35 sites in the US.

Number of Subjects:

Approximately 60 subjects (40 subjects on IDN-6556: 20 on placebo) will be assigned in a 2:1 ratio to IDN-6556 25 mg BID or placebo. Up to 15 subjects with an Ishak score of F6 can be enrolled.

Design:

This is a double-blind, randomized, multicenter study involving subjects with chronic HCV who underwent liver transplantation; developed HCV-related liver fibrosis or cirrhosis; achieved a sustained virologic response (SVR) following anti-HCV therapy;

Title: A Multicenter, Double-Blind, Randomized Trial of IDN-6556 in Subjects Who had Hepatitis C Virus (HCV) Reinfection and Liver Fibrosis or Cirrhosis following Orthotopic Liver Transplantation for Chronic HCV Infection and Who Subsequently Achieved a Sustained Virologic Response Following anti-HCV Therapy

[figure not shown]
and still show demonstrable fibrosis or cirrhosis on liver biopsy. Upon successful screening, subjects will be randomized to receive 25 mg BID of IDN-6556 or placebo in a 2:1 ratio.

The randomization will be stratified based on the stage of fibrosis or cirrhosis at Baseline:

1. Ishak F2
2. Ishak F3 – F5
3. Ishak 6

The study treatment duration will be two years. All subjects who complete or discontinue from the study, for any reason, will have a follow-up visit four weeks after the end of treatment visit. Subjects who complete the study will have a liver biopsy performed at M24. Subjects who discontinue the study prematurely will be contacted and asked to sign a separate consent to return for a Month 24 liver biopsy (primary endpoint).

Schema:

*A biopsy must be conducted if previous biopsy (bx) was >3 months prior to Day 1 or if tissue is not available.

Title: A Multicenter, Double-Blind, Randomized Trial of IDN-6556 in Subjects Who had Hepatitis C Virus (HCV) Reinfection and Liver Fibrosis or Cirrhosis following Orthotopic Liver Transplantation for Chronic HCV Infection and Who Subsequently Achieved a Sustained Virologic Response Following anti-HCV Therapy

Dosage and Administration:

IDN-6556 will be double-blind with matching placebo. 25 mg of IDN-6556 or placebo will be administered orally twice a day, preferably with food.

Drug Supply:

IDN-6556 will be supplied in bottles containing 60 capsules, each containing 25 mg of IDN-6556. Matching placebo will be supplied in bottles containing 60 capsules.

Subject Entry Criteria (Refer to protocol **Sections 7.1 and 7.2** for full entry criteria)

Key Inclusion Criteria:

1. Male or female subjects of minimum adult legal age (according to local laws for signing the informed consent document), able to provide written informed consent, and able to understand and willing to comply with the requirements of the study
2. History of orthotopic liver transplantation for HCV-induced liver disease
Note: Living donor or cadaveric transplantation will be permitted into the study. HCV positive donor livers will also be permitted into the study.
3. Diagnosis of HCV infection (HCV-RNA detectable in serum) and liver fibrosis or cirrhosis status post liver transplantation, and achieved a sustained virologic response (SVR) with anti-viral HCV treatment within 18 months of Day 1
Note: For the purposes of this study, subjects must meet the definition of SVR as defined by the anti-HCV regimen used.
4. Liver fibrosis or cirrhosis on liver histology as read by central histopathologist of Ishak F2 to F6 within three months of Day 1
Note: Baseline liver histology in close approximation of the three month window may be permitted on a case by case basis after discussion with the Medical Monitor.
5. Willingness to utilize two reliable forms of contraception (for both males and females of childbearing potential) from Screening to one month after the last dose of study drug

Key Exclusion Criteria:

1. Known active infection with hepatitis B virus (HBV) and/or human immunodeficiency virus (HIV)
2. History of renal transplant and/or severe renal impairment defined as eGFR (estimated glomerular filtration rate) of less than 30 mL/min/1.73 m²
3. Evidence of tumor burden >Milan criteria, or evidence of micro- or macrovascular invasion in explanted liver
4. Hepatocellular carcinoma (HCC) at entry into the study
5. Concurrent sirolimus (rapamycin) use

Title: A Multicenter, Double-Blind, Randomized Trial of IDN-6556 in Subjects Who had Hepatitis C Virus (HCV) Reinfection and Liver Fibrosis or Cirrhosis following Orthotopic Liver Transplantation for Chronic HCV Infection and Who Subsequently Achieved a Sustained Virologic Response Following anti-HCV Therapy

6. History or presence of clinically concerning cardiac arrhythmias, or prolongation of Screening (pre-treatment) QTcF interval of > 480 milliseconds (msec)
7. Subjects with diagnosed or suspected systemic lupus erythematosus (SLE) and/or rheumatoid arthritis (RA)
8. If female: known pregnancy, positive urine or serum pregnancy test, or lactating/breastfeeding.

Criteria for Evaluation:**Safety Variables:**

Safety evaluations will be based on adverse event (AE) reports. These will be coded using MedDRA to preferred terms, sorted by body system, and compared between the two treatment groups.

1. Serious adverse events will be analyzed separately
2. Clinical laboratory variables will be evaluated in the context of coinciding clinical adverse events when necessary

Efficacy Variables:Efficacy Endpoints:

- Ishak Fibrosis Score
- Necro-inflammatory sub-score of the modified Histological Activity Index
- Biomarkers of apoptosis
- Liver function (e.g., ALT, AST, bilirubin)
- Transient elastography (to be performed at select centers only)

Exploratory Endpoint:

- Morphometric image analysis to quantify collagen deposition

Statistical Methods:

All endpoints will be tested at a two-sided statistical significance level of 0.05.

For the comparison of Ishak Fibrosis Scores at 24 months, subjects will be classified into one of the following three categories:

- Category 1. Regression at 24 months defined as a greater than or equal to a one point improvement in Ishak Fibrosis Score from Baseline.
- Category 2. Stable disease at 24 months defined as no change from Baseline in the Ishak Fibrosis Score from Baseline.

Title: A Multicenter, Double-Blind, Randomized Trial of IDN-6556 in Subjects Who had Hepatitis C Virus (HCV) Reinfection and Liver Fibrosis or Cirrhosis following Orthotopic Liver Transplantation for Chronic HCV Infection and Who Subsequently Achieved a Sustained Virologic Response Following anti-HCV Therapy

- Category 3. Progression at 24 months defined as a greater than or equal to a one point worsening from Baseline in the Ishak Fibrosis Score from Baseline or death/re-transplantation

Changes in the Ishak Fibrosis Score at 24 months will be analyzed by a logistic regression model, appropriate for the analysis of ordinal categorical data, to derive the odds ratio and associated 95% confidence interval for IDN-6556 against placebo. The model will allow adjustment for the following variables:

- Baseline Ishak Fibrosis Score
- Immunosuppression regimen (classified into one of five groups: tacrolimus with/without steroids; cyclosporine with/without steroids; other)
- Age of the transplant donor
- Age of the recipient

Adverse events, vital signs, ECGs, liver and abdominal ultrasounds, and routine laboratory test data will be explored through the use of standard presentations of descriptive statistics.

Title: A Multicenter, Double-Blind, Randomized Trial of IDN-6556 in Subjects Who had Hepatitis C Virus (HCV) Reinfection and Liver Fibrosis or Cirrhosis following Orthotopic Liver Transplantation for Chronic HCV Infection and Who Subsequently Achieved a Sustained Virologic Response Following anti-HCV Therapy

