8.2.3 Additional

Effects on biomarkers of mechanism of action and inflammation, and liver function will be evaluated as additional endpoints.

Title: A Multicenter, Double-Blind, Randomized Trial of IDN-6556 in Subjects Who had Hepatitis C Virus (HCV) Reinfection and Liver Fibrosis or Cirrhosis following Orthotopic Liver Transplantation for Chronic HCV Infection and Who Subsequently Achieved a Sustained Virologic Response Following anti-HCV Therapy

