2.2 SECONDARY OBJECTIVES

The secondary objectives of this clinical trial are:

- To determine the effects of oral emricasan on necro-inflammatory sub-score of the modified Histological Activity Index
- To determine the effects of oral emricasan on markers of mechanism of action and inflammation
- To assess the safety and tolerability of oral emricasan in subject's status post orthotopic liver transplantation.

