4 PLANNED SIZE DETERMINATION

This study will be conducted at multiple centers at which approximately 60 subjects will be enrolled and treated in a 2:1 ratio with emricasan or placebo, respectively. The sample size determination for this study is based on the Phase 2b screening methodology presented in [Fleming and Richardson \(2004\)](#).

The base case for the placebo response rate of 30% was assumed and obtained from [George, et al \(2009\)](#), where it stated that 29% of patients showed a response in fibrosis from a mean of 1.6 years following HCV-SVR.

Treatment duration for all subjects is expected to be two years. The primary analysis of this Phase 2 “screening” study is formally based on a three-category decision guideline. The decision guideline for this study is based on whether the difference in the proportions of subjects who show a response (i.e., improvement or no change) per their Ishak Fibrosis Score at 24 months for emricasan compared to placebo is less than 5%, is from 5% up to 15%, or is more than 15%. Specifically, the outcome of the study will determine one of the following three course of action:

1. If the difference in response rates between emricasan and placebo (i.e., emricasan response rate – placebo response rate) is less than 5%, then emricasan regimen is not plausibly more efficacious than placebo; hence, emricasan or its utility in this indication will be reconsidered.
2. If the difference in response rates between emricasan and placebo is from 5% up to 15%, then emricasan is plausibly more efficacious than placebo in this indication if secondary analyses of biomarkers suggest utility of emricasan or a positive safety profile is observed; hence, emricasan could be evaluated in a subsequent Phase 3 clinical study.
3. If the difference in response rates between emricasan and placebo is more than 15%, then emricasan could be evaluated in a subsequent Phase 3 study.

These categories should not be interpreted as providing strict decision rules but rather as guidelines that will be factored into a broader scientific assessment of the benefit to risk profile for emricasan in this indication. This broader assessment will include consideration of secondary efficacy analyses, safety profile, and relevant information external to this study.

The operating characteristics for this three-category decision guideline are shown in Table 1.

Table 1. Operating Characteristics for Three-Category Decision Guideline

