9.2 SECONDARY EFFICACY ANALYSES

All secondary analyses will be conducted using the FAS. All secondary endpoints based on the Months 12 and 24 liver biopsies will include data as collected (per [Section 3.5](#)). All secondary endpoints will be summarized using observed cases.

No multiplicity adjustments will be made for the analysis of secondary endpoints.

9.2.1 Secondary Efficacy Analysis: Testing the Difference in Response Rates Stratified by Baseline Ishak Fibrosis Score

Testing of differences in response rates will be conducted using a Cochran-Mantel-Haenszel test. For each of the analyses described in [Section 9.1](#) above, the testing will be stratified separately by each of the following:

- Baseline Ishak fibrosis score strata (F2, F3-F5, F6)
- Baseline Ishak fibrosis score grouping A (F2-F3, F4-F6)
- Baseline Ishak fibrosis score (F2-F6)

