9.2.5 Secondary Efficacy Analysis: Biomarkers

Biomarker endpoints will be summarized descriptively at each visit by treatment group. Change from baseline values for each biomarker at each post-baseline visit will be summarized descriptively by treatment group. If log-transformations are applied to any of the biomarker endpoints, the geometric mean, coefficient of variation, and percent relative change will also be included in the descriptive statistics.

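### Biomarkers and liver stiffness have no planned between-arm estimate or CI, although the protocol says all endpoints are tested and biomarkers inform the middle decision category

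*Protocol*

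**What the plan says.** The protocol synopsis, under Statistical Methods, states "All endpoints will be tested at a two-sided statistical significance level of 0.05". Its list of efficacy endpoints includes "Biomarkers of apoptosis", liver function and transient elastography at selected centers. The synopsis reserves descriptive presentation for adverse events, vital signs, ECGs, ultrasounds and routine laboratory data. Protocol 8.2.3 ranks the markers lower: "Effects on biomarkers of mechanism of action and inflammation, and liver function will be evaluated as additional endpoints". Protocol 12.6.3 names no biomarker test or model.

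SAP 2.2 has as a secondary objective "To determine the effects of oral emricasan on markers of mechanism of action and inflammation", and SAP 5.2.4 and 5.2.5 place biomarkers and liver stiffness among the secondary efficacy endpoints. For the analysis, SAP 9.2.5 says "Change from baseline values for each biomarker at each post-baseline visit will be summarized descriptively by treatment group". If a log transform is used, the geometric mean, coefficient of variation and "percent relative change will also be included in the descriptive statistics". SAP 9.2.7 treats liver stiffness in the same descriptive way. The between-arm test that SAP 9.2 names is for histological response only: "Testing of differences in response rates will be conducted using a Cochran-Mantel-Haenszel test".

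Biomarkers also appear in the decision guideline. In protocol 12.5, supportive biomarkers are the stated condition for going on to Phase 3 from category 2 (an estimated gain of 5% up to 15%). In SAP 4 the same category leads on "if secondary analyses of biomarkers suggest utility of emricasan", and that sentence continues with a positive safety profile as an alternative route.

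**The concern.** An objective to determine an effect calls for a contrast between emricasan and placebo with a measure of its uncertainty. The SAP provides neither for these markers. The protocol sentence does not name the contrast, but in a two-arm placebo-controlled trial the natural reading of testing is active against placebo.

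SAP 14.1 lists the changes from the protocol and describes everything else as added detail and clarity. Dropping between-arm inference for a group of efficacy endpoints is more than that, and it is not listed.

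At stake is how the biomarker condition would be judged if the response difference falls in category 2. No marker, visit, scale or contrast is fixed in advance, and neither document says what would count as support. A favourable direction in one of several sets of arm means could then be read as evidence.

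**Working it through.** **1. Protocol against SAP**

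- Apoptosis biomarkers: tested at two-sided 0.05 (synopsis); arm-level values and changes only (SAP 9.2.5).
- Elastography: tested at two-sided 0.05 (synopsis); arm-level values and changes only (SAP 9.2.7).
- ALT and AST: covered by the same synopsis sentence as liver function. They are also routine laboratory tests, so the synopsis's descriptive sentence could be read to cover them.
- Change log (SAP 14.1): mentions observed cases for secondary analyses, with nothing about testing.
- Same pattern elsewhere: protocol 12.6.3 promises effect estimates with 95% CIs for the histological activity score, while SAP 9.2.3 gives component summaries and shift tables.

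**2. How often category 2 arises**

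Inputs: 40 and 20 subjects (SAP 3.3) and a 30% placebo rate (SAP 4). The probability of a band is the sum, over all x of 40 and y of 20, of Bin(x; 40, 0.30 + TE) × Bin(y; 20, 0.30) where x/40 − y/20 lies in the band.

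- TE 0: 67.4 / 21.6 / 11.0%; the plan states 67 / 22 / 11%.
- TE 15: 22.8 / 23.8 / 53.4%; the plan states 23 / 24 / 53%.

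Every cell agrees within 0.5 point when ties at exactly 5 and 15 points are left to floating-point arithmetic. The stated middle band is 22, 26, 27 and 24% for TE 0, 5, 10 and 15. With ties handled exactly (above 5% up to and including 15%), it is 22% to 30% for TE 0 to 20.

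**3. Precision of a biomarker contrast**

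The documents give no biomarker SD, so results are in SD units.

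- SE = √(1/20 + 1/40) = 0.274 SD.
- 95% CI half-width = 1.96 × 0.274 = 0.54 SD.
- Difference detectable with 80% power at two-sided 0.05 = (1.96 + 0.84) × 0.274 = 0.77 SD.
- With an assumed 10% or 20% of values missing (36 and 18, or 32 and 16), the half-width is 0.57 or 0.60 SD.

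**4. Gain from baseline adjustment**

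Assume equal SDs at baseline and follow-up, with correlation r. The variance of a change score is proportional to 2(1 − r), and that of a baseline-adjusted analysis to 1 − r². Their ratio is (1 + r)/2, so the reduction is (1 − r)/2. At assumed r of 0.3, 0.5 and 0.7 this is 35%, 25% and 15%. The documents give no r.

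**5. Why a lead marker is needed**

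Six biomarkers (SAP 5.2.4) plus liver stiffness at two visits make 7 × 2 = 14 intervals, and SAP 9.2 makes no multiplicity adjustment. For six markers tested at 0.05 and assumed independent, the chance of at least one false positive is 1 − 0.95⁶ = 26%. Judged by direction alone, with no true effect and an even chance per marker, the chance that at least one of six favours the drug runs from 50% (perfect correlation) to 1 − 0.5⁶ = 98% (independence).

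**The case against.** The strongest reply is that the synopsis sentence sets a significance level and no more. The protocol specifies no biomarker analysis, ranks the markers as additional, allows descriptive methods where appropriate (12.6.1) and lets the SAP modify the plan (12.1). This stands in part: no specified analysis was breached. What remains is a general commitment that the SAP does not meet and does not record as changed.

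A reader might infer that the whole category 2 decision rests on no estimate of treatment effect. The documents do not support that. Category 2 is entered on the response-rate difference, which SAP 9.1 reports with a 95% CI. Within it, the SAP accepts a positive safety profile in place of biomarkers. Both documents call the categories guidelines, to be weighed with other evidence.

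A reader might also infer that nobody could tell whether a biomarker difference exceeds chance. That too goes too far. The planned n, mean and SD of change by arm, together with subject listings, allow a crude unadjusted difference and interval. What is missing is a prespecified contrast, scale and visit, and baseline adjustment.

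Finally, confidence intervals alone would not remove subjectivity, because 14 unadjusted intervals can be read selectively. This objection stands, and the fix answers it by naming a lead marker and visit.

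**Conclusion.** The point holds in limited form. The secondary objective on mechanism and inflammation markers has no prespecified between-arm estimate or CI, liver stiffness has none either, and the departure from the synopsis is unrecorded. The biomarker condition in category 2 is the stated condition in the protocol and one of two alternatives in the SAP; in both it lacks a defined comparison.

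On the plan's figures this could matter in 22% to 27% of trials with a true effect of 0 to 15 points. That range depends on the 30% placebo rate behind the table. The SAP carries the protocol's table over unchanged, although its response definition also counts stable disease for baseline F2 to F5.

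The size of the gain from baseline adjustment depends on a correlation the documents do not give. Because 80% power needs a true difference of about 0.77 SD, estimates with intervals will serve better than significance tests. This should be corrected before database lock, but it does not affect the primary analysis.

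**What to change.** In SAP 9.2.5, add an analysis of covariance for each biomarker at Months 12 and 24 (log scale where skewed), with treatment, baseline value and randomisation stratum as terms. Report the adjusted difference, or the ratio of geometric means, with its 95% CI. State which baseline applies to ALT and AST, since SAP 7 defines baseline differently for laboratory summaries and for other analyses.

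Name in advance the one marker and visit that will inform the biomarker condition in category 2, and say what result would count as support. Label the remaining intervals exploratory and unadjusted for multiplicity.

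Add the same model to SAP 9.2.7 for liver stiffness, noting that it covers a subset at seven sites (SAP 5.2.5), so its intervals will be wider.

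Record in SAP 14.1 how the analysis departs from the synopsis sentence.

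The cost is a few more tables and a paragraph of text. The data are already scheduled: biomarkers at Day 1 and Months 12 and 24, elastography at Screening and Months 12 and 24 at the selected centers, and stratum from randomisation. The drawback is limited precision, which the report should state.

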2.0 LIST OF ABBREVIATIONS

| | |
|-----------------|--|
| AASLD | American Association for the Study of Liver Diseases |
| AE(s) | adverse event(s) |
| AFP | α -fetoprotein |
| ALT | alanine aminotransferase |
| AST | aspartate aminotransferase |
| BID | bis in die , twice daily |
| BMI | body mass index |
| BUN | blood urea nitrogen |
| Ca | calcium |
| CFR | Code of Federal Regulations |
| C-G | Cockcroft-Gault |
| CIOMS | Council for International Organization of Medical Sciences |
| cCK18 | caspase cleaved cytokeratin 18 |
| Cl | chloride |
| CO ₂ | carbon dioxide |
| CRA | Clinical Research Associate |
| CRF | case report form |
| CRP | c-reactive protein |
| CS | clinically significant |
| CT | computed tomography |
| dL | deciliter |
| DMC | Data Monitoring Committee |
| ECG | electrocardiogram |
| EDC | electronic data capture |
| e.g. | exempli gratia , for example |
| eGFR | estimated glomerular filtration rate |
| ELF | Enhanced Liver Fibrosis |
| EOT | end of treatment |
| ET | early termination |
| FAS | full analysis set |

Title: A Multicenter, Double-Blind, Randomized Trial of IDN-6556 in Subjects Who had Hepatitis C Virus (HCV) Reinfection and Liver Fibrosis or Cirrhosis following Orthotopic Liver Transplantation for Chronic HCV Infection and Who Subsequently Achieved a Sustained Virologic Response Following anti-HCV Therapy

| | |
|--------|--|
| FDA | US Food and Drug Administration |
| fICK18 | full length cytokeratin 18 |
| g | gram(s) |
| GCP | good clinical practice |
| GFR | glomerular filtration rate |
| GGT | gamma-glutamyl transferase |
| GMP | good manufacturing practice |
| HBV | hepatitis B virus |
| HCC | hepatocellular carcinoma |
| HCG | human chorionic gonadotropin |
| Hct | hematocrit |
| HCV | hepatitis C virus |
| Hgb | hemoglobin |
| HIV | human immunodeficiency virus |
| IB | investigator's brochure |
| IBC | iron binding capacity |
| ICF | informed consent form |
| ICH | International Conference on Harmonisation |
| ICMJE | International Committee of Medical Journal Editors |
| i.e. | id est , that is |
| IEC | Independent Ethics Committee |
| IMP | investigational medicinal product |
| INR | international normalized ratio |
| IRB | Institutional Review Board |
| ITT | intention-to-treat |
| IWRS | Interactive Web Randomization System |
| LDH | lactate dehydrogenase |
| MCH | mean corpuscular hemoglobin |
| MCHC | mean corpuscular hemoglobin concentration |
| MCV | mean corpuscular volume |
| mg | milligram |
| MedDRA | Medical Dictionary for Regulatory Activities |

Title: A Multicenter, Double-Blind, Randomized Trial of IDN-6556 in Subjects Who had Hepatitis C Virus (HCV) Reinfection and Liver Fibrosis or Cirrhosis following Orthotopic Liver Transplantation for Chronic HCV Infection and Who Subsequently Achieved a Sustained Virologic Response Following anti-HCV Therapy

| | |
|---------|---|
| MDRD | Modification of Diet in Renal Disease |
| Mg | magnesium |
| mL | milliliter |
| mm | millimeter |
| MPV | mean platelet volume |
| MRI | magnetic resonance imaging |
| msec(s) | millisecond(s) |
| Na | sodium |
| NAFLD | non-alcoholic fatty liver disease |
| NASH | non-alcoholic steatohepatitis |
| NCS | not clinically significant |
| OTC | over-the-counter |
| pH | hydrogen ion concentration |
| POLT | post orthotopic liver transplantation |
| PP | per-protocol |
| QD | quaque die , once daily |
| RA | rheumatoid arthritis |
| RBC | red blood cell |
| RNA | ribonucleic acid |
| SAE(s) | serious adverse event(s) |
| SAP | statistical analysis plan |
| sec(s) | second(s) |
| SLE | systemic lupus erythematosus |
| SOP | standard operating procedure |
| SUSAR | suspected unexpected serious adverse reaction |
| SVR | sustained virologic response |
| SVR4 | sustained virologic response 4 weeks after therapy |
| SVR24 | sustained virologic response 24 weeks after therapy |
| ULN | upper limit of normal |
| USA | United States of America |
| WBC | white blood cell |

Title: A Multicenter, Double-Blind, Randomized Trial of IDN-6556 in Subjects Who had Hepatitis C Virus (HCV) Reinfection and Liver Fibrosis or Cirrhosis following Orthotopic Liver Transplantation for Chronic HCV Infection and Who Subsequently Achieved a Sustained Virologic Response Following anti-HCV Therapy

